11.2 ANALYSIS

In this pilot randomized control study, changes in measurements from baseline to intra-study to exit will be assessed. Participants will serve as their own controls and comparisons will be made to no change. One sample t-test will be used for numerical data. Fisher's Exact or Chi square tests will be used for categorical data. Analyses will be conducted to calculate mean (SD) for normally distributed variables for actual data or mean (SE) for modeled data and median (interquartile range) values in instances of non-normally distributed variables. McNemar test will be used for 2-category match-paired data. Cohen kappa statistic will be used for 3-category match-paired data. Statistical significance is set at $P < .05$. All deviations from the study protocol will be identified, recorded and analyzed.

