	
180 adult participants (up to 90 in each arm) who report daily smoking of 5 cigarettes or more. The study will be performed remotely on an ambulatory basis. Participants will be asked to setup and use their assigned program (Pivot for intervention or QuitGuide for control). Both study arms include the option for participants to order FDA-approved nicotine replacement therapy (NRT). The study duration is 104 weeks, with the estimated active time using the program of up to 6 months and the time thereafter as follow-up. Participants will receive online questionnaires at intervals throughout the study and may undergo up to 4 videocall biovalidation study visits in which they provide breath samples using a personal carbon monoxide (CO) breath sensor, which measures CO in exhaled breath.

Data Collection	Data will be collected through participant completion of emailed online questionnaires.
Performance Variables	
Comparison between the two smoking cessation programs on:
 
 • User engagement and retention in the program • Attitudes towards quitting: desire to quit, confidence to quit, self-efficacy and difficulty to stay quit • Smoking behavior: quit attempts, change in cigarettes per day (CPD), smoking cessation via 7-and 30-day PPA (self-report and biochemically confirmed), continuous abstinence (self-report and biochemically confirmed), abstinence from all tobacco products (self-report), use of NRT • Participant feedback on the set-up, use experience, design and impact on their assigned smoking cessation program, and use of other (non-study) smoking cessation tools
Performance Endpoint and Analysis	Change from baseline measurement

Contents

1.	List of Abbreviations	7
2.	Introduction.....	8
2.1	Background	8
2.2	Study Rationale	10
2.3	Potential Risks and Benefits.....	10
2.3.1	Known Potential Risks	10
2.3.2	Known Potential Benefits.....	11
2.3.3	Risk Benefit Assessment	11
3.	Objectives	11
4.	Definitions.....	12
5.	Control – QuitGuide Plus Nicotine Replacement Therapy.....	13
5.1	QuitGuide	13
5.2	Nicotine Replacement Therapy	13
6.	Intervention - Pivot	13
6.1	Pivot Breath Sensor	13
6.1.1	Indications for Use	14
6.2	Labeling and Packaging	14
6.3	Pivot Breath Sensor Submitting a Breath Sample (Specific Steps)	14
6.4	CO Log.....	15
6.5	Pivot App.....	16
6.6	Pivot Coaching	17
6.7	Pivot Nicotine Replacement Therapy (NRT).....	17
6.8	Pivot Moderated Online Community	17
7.	Study Design and Overview	17
7.1	Study Design	17

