7.3 STUDY OUTCOMES

- User engagement and retention in the program (number of app opens, number of days with at least one app open, number of weeks with at least one app open)
- Attitudes towards quitting: desire to quit, confidence to quit, difficulty to quit and self-efficacy
- Smoking behavior: quit attempts, change in cigarettes per day (CPD), smoking cessation via 7-and 30-day PPA (self-report and biochemically confirmed), continuous abstinence (self-report and biochemically confirmed), abstinence from all tobacco products, use of NRT
- Participant feedback on the set-up, use experience, design and impact of their assigned smoking cessation program

Outcomes include:

Primary:

- Total app opens in Pivot vs QuitGuide at 12 weeks (3 months)

Secondary:

- Change in expected difficulty in staying quit (participant self-report, scale 1-10) at 2, 4, 8, 12 weeks after enrollment
- Change in confidence levels towards quitting smoking (expected success in quitting, participant self-report, scale 1-10) at 2, 4, 8, 12 weeks after enrollment
- Desire to quit (yes/no) at 4 weeks after enrollment
- Self-reported abstinence (7-day and 30-day PPA) at 6, 8, 12, 26, 52 and 104 weeks after enrollment
- Self-reported abstinence (7-day PPA) at 2 and 4 weeks after enrollment
- Self-reported abstinence from all tobacco products at 6, 8, 12, 26, 52, and 104 weeks after

enrollment

- Biochemically confirmed abstinence at 12, 26, 52, and 104 weeks
 - To be considered biochemically abstinent:
 - Breath CO sample should be less than 10 ppm [16]
- Self-reported continuous abstinence at 26, 52 and 104 weeks, defined as a self-report of smoking no more than five cigarettes from 12 weeks after enrollment
 - 12 weeks is chosen because it allows for a full course of NRT, and it has been standard in studies that include pharmacotherapy for smoking cessation [17]
- Biochemically confirmed continuous abstinence at 26, 52, and 104 weeks, defined as a self-report of smoking no more than five cigarettes from 12 weeks after enrollment, and confirmation on all previous and present biovalidation tests:
 - Breath CO sample should be less than 10 ppm for participant to be considered abstinent [16]
- The proportion of participants who reduced their cigarettes per day (CPD) by $\geq 50\%$ compared to baseline at 4, 12, 26, 52 and 104 weeks

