7.5 PARTICIPANT RANDOMIZATION, STRATIFICATION AND ENROLLMENT

After signing the ICF, the participant will complete an online Baseline Questionnaire. Based on responses to the questionnaire, participants will be randomly assigned in a computer-generated 1:1 manner to either Pivot or QuitGuide using randomly permuted blocks of size 2 and 4, stratified by daily smoking frequency (≤ 14 vs ≥ 15 cigarettes per day), employment status (full-time or part-time employment vs unemployed), race/ethnicity (minority race/ethnicity vs non-Hispanic White), and expected difficulty staying quit (scale 1-10; self-reported score of ≤ 5 vs. ≥ 6). After randomization, participants will be emailed the link to access their assigned group. In both groups, participants will be able to access their assigned study app from the moment of randomization and beyond (ie, after the end of the 2-year study period).

Participants will be considered enrolled after completing the following 3 tasks: electronically signing the informed consent form, completing the Baseline Questionnaire and reporting the date they first logged in to their assigned app. If participants do not complete all three criteria, they may be removed from the study.

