7.7 SAMPLE SIZE AND JUSTIFICATION

As this is a pilot RCT and first assessment of Pivot compared to usual care, the study's sample size is powered to show differences in engagement, operationalized as the number of times participants open their assigned app. Previous clinical studies assessing Pivot have reported a mean of 24.2-38.7 app opens (SD range 20.8-25.9) by 90 days (data on file). In addition, Bricker et al. reported app opens comparing ACT-based smoking cessation apps (SmartQuit and iCanQuit) to QuitGuide. In one study, at 2-month follow-up, Bricker et al. reported mean (SD) app opens were 37.2 (46.1) for SmartQuit and 15.2 (13.6) for QuitGuide.[10] In a subsequent study, at 12-month follow-up, mean (SD) app opens were 37.5 (88.4) for iCanQuit and 9.9 (50.0) for QuitGuide.[11] Based on this data, we estimate mean (SD) 25 (25) app opens in the intervention arm vs. 15 (19) app opens in the control arm at 12 weeks. To detect a difference of 10 app opens or greater between Pivot and QuitGuide with 0.8 power and 0.05 alpha would require 156.7 participants, which we round up to 158. In a previous study, 272/319 (85.3%) participants completed the end-of-Pivot questionnaire at a mean (SD) 4.1 (1.4) months after enrollment. [13,14] Considering that we will assess our primary endpoint at 3 months (12 weeks), we are accordingly including an expected 15% attrition rate, with a plan to enroll up to 180 participants (up to 90 in each arm).

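### Section 11.2 names no between-arm test for the primary outcome: its only test for numerical data is one-sample, against no change

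*Combined protocol and SAP*

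**What the plan says.** Section 7.3 and the synopsis define the primary outcome as total app opens at 12 weeks, Pivot against QuitGuide. Section 7.7 sizes the trial on that contrast: "To detect a difference of 10 app opens or greater between Pivot and QuitGuide with 0.8 power and 0.05 alpha", with the planning values "we estimate mean (SD) 25 (25) app opens in the intervention arm vs. 15 (19) app opens in the control arm at 12 weeks". Under Performance Variables, the synopsis announces a "Comparison between the two smoking cessation programs on" user engagement, among other things.

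Section 11.2 is the only analysis text. It opens by saying that changes from baseline through to exit will be assessed, and continues: "Participants will serve as their own controls and comparisons will be made to no change. One sample t-test will be used for numerical data". It then lists Fisher's exact or chi-square for categorical data, McNemar for paired two-category data and Cohen's kappa for paired three-category data. It does not mention app opens. The synopsis line on the performance endpoint and its analysis has the same within-person framing: "Change from baseline measurement".

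**The concern.** Followed literally, 11.2 never produces the randomised comparison for the primary outcome or for any other numerical outcome. The app is assigned only after the Baseline Questionnaire, so app opens have no baseline to change from. The one null value left for a one-sample test is zero opens. Enrolment excludes that value in both arms, because it requires "completing the Baseline Questionnaire and reporting the date they first logged in to their assigned app" (Section 7.5).

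Confidence and expected difficulty do have baselines, so a within-arm test of change is coherent for them. It still does not estimate the program effect: it mixes that effect with the natural course of people selected because they plan to quit within 30 days.

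What is at stake is pre-specification. The arms, data and sample size are all in place for a between-arm comparison, but nothing commits the sponsor to one method. The trial is open-label and sponsor-run, and the counts will be skewed, so a mean-based and a rank-based test can give different answers.

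**Working it through.** **Inputs.** From 7.7: means (SDs) 25 (25) and 15 (19), difference 10, alpha 0.05, power 0.80, 15% attrition, up to 90 per arm. From 7.5: 1:1 allocation. Neither 7.7 nor 11.2 states sidedness; two-sided is an assumption, which step 1 supports.

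**1. The plan's own figure.**
- Pooled SD = √((25² + 19²)/2) = √493 = 22.20, so the standardised difference is 10/22.20 = 0.450.
- Normal approximation: total = 2 × (625 + 361) × (1.960 + 0.842)² / 10² ≈ 154.8.
- Two-sample t-test, two-sided, noncentral t: 78.36 per arm, **156.72 in total**. Section 7.7 states 156.7.
- The Welch version gives 156.86. A one-sided normal approximation gives 122, which does not match.

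**2. Could the test named in 11.2 have produced that figure?** A one-sample t-test for a shift of 10 at 80% power needs about 30 participants (SD 19), 41 (SD 22.2) or 51 (SD 25). It cannot give 156.7.

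**3. What a one-sample test would show.** Against zero opens, for QuitGuide with about 76 evaluable, the noncentrality is (15/19) × √76 = 6.88, and power exceeds 0.9999. For Pivot with 79, it is (25/25) × √79 = 8.89, and power again exceeds 0.9999. Both arms would be significant even if the programs were equal.

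**4. Why the choice of between-arm test matters.** For a variable that cannot be negative, skewness is at least CV − 1/CV, where CV = SD/mean. Enrolled participants have at least one open, so subtract 1 from each count:
- Pivot: CV = 25/24 = 1.042, skewness at least 1.042 − 0.960 = 0.08.
- QuitGuide: CV = 19/14 = 1.357, skewness at least 1.357 − 0.737 = 0.62.

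These are lower bounds. Right skew follows from the planning values themselves.

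**5. Size of the effect, by simulation.** There were 20,000 trials per setting, with 77 per arm (0.85 × 90 = 76.5), counts of at least 1, and distributions matched to the planning means and SDs. The documents give no distribution, so two shapes were assumed.

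| Setting | Welch | Mann-Whitney | Disagree on significance |
|---|---|---|---|
| 25 (25) vs 15 (19), negative binomial | 0.802 | 0.934 | 0.146 |
| 25 (25) vs 15 (19), log-normal | 0.827 | 0.992 | 0.166 |
| No difference, either shape | 0.043-0.048 | 0.048-0.051 | – |

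With no difference, the smaller of the two p-values fell below 0.05 in 7.1-7.3% of trials. Repeat simulations gave 7.0-7.6% for this rate and 14-17% for disagreement under the planned effect.

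**The case against.** The best defence is that 11.2 omits the primary analysis rather than contradicting it. Its opening sentence concerns changes from baseline, and the one-sample test can be read as confined to those. App opens are not a change score, and no passage proposes testing them against zero. That reading is possible, but the sentence on numerical data carries no such limit. Even on that reading, the plan has no analysis of its primary outcome.

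Several narrower points stand:
- The provision for medians, "values in instances of non-normally distributed variables", concerns descriptive summaries and does not switch tests. The freedom to choose a test comes from the silence of 11.2. That sentence shows only that non-normal data were foreseen.
- The disagreement between tests under the planned effect is almost all one-way. Mann-Whitney alone was significant in 13-17% of trials and Welch alone in at most 0.6%. It is mainly a power gap.
- The 7.0-7.6% error rate supposes an analyst who runs both tests and reports the smaller p-value. Nothing in the documents suggests this, and the arithmetic in 7.7 would make a departure from a t-test visible.
- Fisher's exact and chi-square are independent-sample tests and would naturally compare arms. Asking 11.2 to say so is a clarification.

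The reference in 11.2 to modeled data fixes only a summary format (mean and SE). It specifies no model, covariates or contrast. Nothing in 11.2 is marked as redacted, and no separate SAP is mentioned. The pilot label does not remove the point either, because 7.7 powers a formal hypothesis test.

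**Conclusion.** The concern holds, and it must be fixed. Section 11.2 specifies no between-arm analysis of the numerical primary outcome, and the one numerical test it names cannot address that outcome. The match of 156.72 to the stated 156.7 shows that the sizing assumed a two-sided two-sample t-test. The fault therefore lies in the analysis text, not in the basis of the sample size.

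The cost is lost pre-specification, not lost data. The error inflation is modest (about 5% to 7.0-7.6%). It rests on two assumed distributions, on 77 per arm, and on a choice between just two tests. The main conclusion needs none of these assumptions, because it follows from comparing 11.2 with 7.3, 7.5 and 7.7.

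**What to change.** In 11.2, name one two-sided between-arm primary test of total app opens at 12 weeks, by randomised arm, and report the difference in means with a 95% confidence interval. A Welch t-test matches the sizing in 7.7. A linear model with robust standard errors, adjusted for the four stratification factors in 7.5, would also serve, but only one may be primary. Because of the skew, pre-specify one sensitivity analysis (a rank test or a count model) and state that it cannot replace the primary.

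The same edit should:
- analyse numerical secondary outcomes that have a baseline as between-arm differences in change;
- state that Fisher's exact and chi-square compare the arms;
- keep one-sample and McNemar results as within-arm description;
- change the synopsis line on the performance endpoint to match;
- say how randomised people with no reported first log-in are handled, since 7.5 allows their removal and 10.1 makes a reported first opening a condition for accepting data.

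The cost is rewording 11.2 and one synopsis line, with that last statement kept consistent with 7.5 and 10.1. Sample size and data collection do not change.

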- Number of quit attempts at 4, 12, 26, 52, and 104 weeks (defined as answering ≥ 1 to the following question: “Since you began the study, how many times have you tried to quit smoking where you've gone at least 1 day without smoking a cigarette, even a single puff?”).
- User satisfaction with the smoking cessation program (set-up and getting started with program, recommend to friend, program design, program was useful for quitting, program helped me quit, program helped me stay quit) at 2, 3, 4, 5, 12, 26, 52 and 104 weeks
- Engagement with program, collected weekly during the first 12 weeks after enrollment:
 - Number of times app opened (self-report)
 - Number of days in which app was opened (self-report)
 - Number of weeks in which app was opened (self-report)
- Participant changes in self-efficacy at 6, 12, 26 and 52 weeks
- Participant changes in self-reported health and wellbeing at 26 and 104 weeks
- Self-reported NRT use at 4, 8, 12, 26, 52 and 104 weeks
- Use of other smoking cessation tools (apps, counseling, non-study medications, etc.) at 12, 26, 52, and 104 weeks
- Alcohol use behavior at 12, 26 and 52 weeks (Alcohol Use Disorders Identification Test-Concise or AUDIT-C screening questionnaire, 3 items) [18-20]
- Presence of depressive symptoms screening at 12, 26, and 52 weeks (Center for Epidemiological Studies Depression Scale or CES-D screening questionnaire, 10 items) [11,21-23]
- Living and social environment relating to cigarette smoking at 12, 26 and 52 weeks (live with other adults who smoke, live with romantic partner who smokes, number of close friends who smoke)
- Adverse events at 26, 52 weeks

Eligibility Criteria

The study population comprises current smokers, 21 years of age and above, who own and

regularly use a smartphone and are ready to quit smoking in the next 30 days.

Inclusion Criteria

- 21+ years of age
- Current daily cigarette smokers (at least 5 cigarettes per day) for the past 12 months
- Plans to quit smoking in the next 30 days
- Resident of the United States
- Able to read and comprehend English
- Owns and uses a smartphone compatible with the study app (iPhone 5 and above with operating system iOS 12 and above, or, Android 7.0 and above with operating system Android 7.0 and above)
- Has daily internet access on smartphone
- Comfortable downloading and using smartphone apps
- Willing to sign the Informed Consent Form

Exclusion Criteria

- Pregnancy (self-reported)

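### Section 11.2 states no Pivot-versus-QuitGuide test for abstinence or cigarettes per day; its governing rule, change from baseline against no change, cannot answer the between-program question.

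*Combined protocol and SAP*

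**What the plan says.** The question is put as a comparison of programs. The synopsis row on performance variables opens with "Comparison between the two smoking cessation programs on" and lists smoking behavior beneath it: point prevalence abstinence, continuous abstinence and change in CPD. Section 2.2 states the same aim for the randomized groups.

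The analysis is put differently. Section 11.2, the only analysis section, sets the frame in one sentence: "Participants will serve as their own controls and comparisons will be made to no change". It then names the tests:

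- "One sample t-test will be used for numerical data"
- "Fisher's Exact or Chi square tests will be used for categorical data"
- "McNemar test will be used for 2-category match-paired data"

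Neither arm is named in 11.2, and it gives no between-arm effect measure or confidence interval. The synopsis row on endpoint and analysis reads only "Change from baseline measurement".

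Two features of the design matter here. Entry requires "Current daily cigarette smokers (at least 5 cigarettes per day) for the past 12 months". One of the secondary outcomes in Section 7.3 is "The proportion of participants who reduced their cigarettes per day (CPD) by $\geq 50\%$ compared to baseline", which is itself a change from baseline.

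**The concern.** Every participant smokes daily at entry, so abstinence at baseline is 0% in both arms. The indicator of at least a 50% CPD reduction is also 0 at baseline by definition. Everyone plans to quit within 30 days, and both arms receive an app and optional free nicotine replacement. Against that background, a within-person test against no change asks whether some people in an arm quit. It does not ask whether Pivot changed quitting.

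If 11.2 were applied in that way, two patterns could arise with no true difference between programs. At moderate quit rates both arms would be significant, which says nothing about Pivot. At low rates one arm would often be significant and the other not by chance alone, and that pattern is easily misread as an advantage. Because the text can be read either way for binary outcomes, the choice of test could also be made after the data are seen.

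**Working it through.** **1. The plan's own figure.** Section 7.7 gives 156.7 participants for 25 (SD 25) against 15 (SD 19) app opens, power 0.8, alpha 0.05.

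- Pooled SD = √((25² + 19²)/2) = 22.2; standardized difference = 10/22.2 = 0.450.
- A two-sided, two-sample t-test (noncentral t) needs 78.36 per arm, 156.7 in total. The figure reproduces.
- A one-sided calculation (normal approximation) gives 122 and does not match.

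The trial was therefore sized on a between-arm test that 11.2 does not list.

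**2. McNemar with nobody abstinent at baseline.** Discordant pairs can go only one way. With b abstainers in an arm, exact two-sided P = 2 × 0.5^b.

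- b = 5: P = 0.0625.
- b = 6: P = 0.031.

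Six abstainers in an arm are enough. The continuity-corrected version also crosses at 6 (P = 0.041); the uncorrected version crosses at 4 (P = 0.046).

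**3. How often this happens with no difference between arms.** Inputs:

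- n = 90 per arm (full enrolment, Section 7.7), or 76 per arm (180 × 0.85 = 153, halved and rounded down).
- True abstinence rate p, equal in both arms. This is an assumption. The documents give no control rate; the earlier Pivot cohort had 32.0% (102/319) for 7-day abstinence at the end of the program.

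Formulas: f = P(Bin(n, p) ≥ 6); both arms significant = f²; exactly one = 2f(1 − f).

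| p | n | One given arm, f | Both arms | Exactly one |
|---|---|---|---|---|
| 5% | 76 | 18.0% | 3.2% | 29.5% |
| 5% | 90 | 29.5% | 8.7% | 41.6% |
| 8% | 76 | 57.4% | 33.0% | 48.9% |
| 8% | 90 | 73.5% | 54.0% | 38.9% |
| 10% | 76 | 78.4% | 61.4% | 33.9% |
| 10% | 90 | 89.7% | 80.4% | 18.5% |
| 15% | 76 | 97.9% | 95.8% | 4.1% |
| 15% | 90 | 99.5% | 99.0% | 1.0% |

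At 32% both arms are significant in essentially every trial.

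**4. The between-arm test on the same data.** By full enumeration at 90 per arm and equal rates of 5% to 32%, chi-square rejects in 4.2–5.1% of trials and Fisher's exact in 1.9–3.4%. For an assumed 32% against 15%, chi-square power is 71% (n = 76) to 78% (n = 90). For 32% against 20% it is about 45% at n = 90. The comparison controls error, but its power depends heavily on the unknown control rate.

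**5. CPD as a number.** Entry sets a floor of 5 but does not fix the level, so step 2 does not apply. The relevant fact is that CPD is expected to fall among people planning to quit. For a one-sample t-test with a mean fall of d SDs of change, the noncentrality is d√n. With the same fall in both arms (d is assumed):

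| d | n | Power in one arm | Both arms (squared) |
|---|---|---|---|
| 0.3 | 76 | 73.3% | 54% |
| 0.3 | 90 | 80.4% | 65% |
| 0.5 | 76 | 99.0% | 98% |
| 0.5 | 90 | 99.7% | 99% |

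**The case against.** The strongest reply is that 11.2 never assigns McNemar to abstinence or to CPD reduction. Fisher's exact and chi-square appear as a separate rule for categorical data. These tests usually compare independent groups, and in a two-arm trial the natural groups are the arms. McNemar may have been meant for other items, such as the yes/no desire to quit. The CPD-reduction outcome has no baseline value to pair with, and 0% abstinence at entry makes McNemar an odd choice there. The synopsis, Section 2.2 and the sample size all point to a between-arm intention.

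Most of this stands. A reader might infer that the plan tests abstinence within person and so will find it significant in both arms whatever Pivot does. The documents do not support that. The assignment is unclear rather than made, and significance in both arms depends on the quit rate: at 5%, which is possible for confirmed continuous abstinence, it occurs in only 3–9% of trials. Nor does entry make the null hypothesis for mean CPD false; that part rests on an expected fall. No section says that significance in one arm alone will be claimed as a benefit, and these are secondary outcomes of a pilot sized on engagement.

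The objection does not remove the gap. The sentence that governs 11.2 points to within-person comparison, the Fisher and chi-square rule does not name the arms, and the only test named for numerical data is a one-sample one. The section mentions modeled means but names no model.

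**Conclusion.** The point holds in a limited form. Section 11.2 does not carry out the comparison promised in the synopsis and Section 2.2. For abstinence and CPD reduction the plan is ambiguous; for CPD as a number it names only a within-person test.

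If the within-person reading were followed, with no difference between programs, exact McNemar would be significant in both arms in 96–99% of trials at a 15% rate, falling to 3–9% at 5%. At low rates the problem changes form: exactly one arm is significant in 39–49% of trials at 8% and in about 30–42% at 5%. For mean CPD, a common fall of 0.3 SD makes both arms significant in 54–65% of trials, and 0.5 SD in 98–99%.

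These figures assume equal true rates or falls in the two arms, 76 to 90 analysed per arm, a two-sided 0.05 level (11.2 does not state sidedness) and the exact form of McNemar. That a test against no change cannot compare the programs does not depend on those assumptions.

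**What to change.** Amend Section 11.2 to state that:

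- every abstinence outcome (7-day, 30-day, all-tobacco, biochemically confirmed, continuous) and the CPD reduction of at least 50% are compared between Pivot and QuitGuide at each scheduled visit by Fisher's exact or chi-square, choosing one in advance, with the risk difference and its 95% confidence interval;
- CPD is compared between arms, adjusted for baseline CPD;
- within-arm changes in these outcomes are descriptive, and significance in one arm only is not evidence of a difference between programs.

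Bring the synopsis row on endpoint and analysis into line. The same revision could name the between-arm test for the primary outcome, app opens, which has no baseline and so does not fit the own-control rule either.

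The cost is a change of wording, with no new data, participants or procedures. The small downside is that within-arm significance claims are dropped and the P values will be less favourable.
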